---	--

15) To compare the neutralizing antibody profile to the B.1.351 variant at D01 and D15 in the booster groups and at D36 in the Comparator group.
 
16) To compare the neutralizing antibody profile to the B.1.351 variant at D01 and D15 in the booster groups and neutralizing antibody profile to the D614G strain at D36 in the Comparator Group.
 
17) To assess the neutralizing antibody profile to the D614G strain and to the B.1.351 variant at D29, D91, D181, and D366 overall, and by age group, by priming platform, and by priming vaccine.
 
18) To describe the neutralizing antibody profile to the B.1.351 variant and to the D614G strain at D01 and D15 in adults older than 55 years of age in the booster group, overall, by priming platform, and by priming vaccine.
 
19) To assess the binding antibody profile at D01, D15, D29, D91, D181, and D366 after booster immunization in adults previously vaccinated with COVID-19 vaccines, overall and by age group, by priming platform, and by priming vaccine.
	
Endpoints for secondary objective #19:
 
 • Individual antibody concentration at each predefined time point • Individual antibody fold-rise post-vaccination relative to D01 at each pre-defined post-vaccination time point • 2-fold-rise and 4-fold rise (fold-rise in antibody concentration $[post/pre] \geq 2$ and ≥ 4) at each pre-defined post-vaccination time point relative to D01 • Responders, defined as participants who had baseline values below LLOQ with quantifiable antibody concentration above assay LLOQ at predefined post-vaccination timepoints and participants with baseline values above LLOQ with a 4-fold increase in binding antibody concentration at each pre-defined postvaccination timepoint
---	--

Secondary Immunogenicity-Supplemental Cohort 2

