--	--

11) To describe, in adults 18-55 years previously vaccinated with any COVID-19 vaccine, the immune response a booster dose of CoV2 preS dTM-AS03 (B.1.351) or CoV2 preS dTM-AS03 (D614 + B.1.351).
 
12) To compare the neutralizing antibody profile to the B.1.351 variant at D15 in each study Intervention Group and D36 in the Comparator Group, overall, by priming platform, and by priming vaccine.
 
13) To compare the neutralizing antibody profile against the D614G strain at D15 following a booster dose of CoV2 preS dTM-AS03 (D614 + B.1.351) and at D36 in the Comparator Group.
 
14) To describe, among adults previously primed with CoV2 preS dTM-AS03 (D614) vaccine, the immune response induced by a booster dose of CoV2 preS dTM-AS03 (D614) or CoV2 preS dTM-AS03 (B.1.351) or CoV2 preS dTM-AS03 (D614 + B.1.351) vaccine, overall, by priming dose, and by age.
 
15) To assess the neutralizing antibody profile to the D614G strain at D29, D91, D181, and D366 in each study Intervention Group, overall, by age group, by priming platform, and by priming vaccine.
 
16) To assess the neutralizing antibody to the B.1.351 variant at D29, D91, D181, and D366 in each study Intervention Group, overall, by age group, by priming platform, and by priming vaccine.
 
17) To describe, in adults over 55 years of age, the neutralizing antibody profile to the B.1.351 variant and to the D614G strain at D01 and D15 by Intervention Group, overall, by priming platform, and by priming vaccine.
 
18) To describe in adults previously vaccinated with the Pfizer/BioNTech COVID-19 mRNA vaccine the immune response (as assessed by pseudovirus neutralization assay geometric mean titers and geometric mean titer ratios) to a booster dose of CoV2 preS dTM-AS03 (B.1.351) exploratory formulations, overall and by age stratum.
 
19) To assess the binding antibody profile at D01, D15, D29, D91, D181, and D366 after booster immunization in adults previously vaccinated with COVID-19 vaccines, overall and by age group, by priming platform, and by priming vaccine.
	
 Individual serum neutralization titer fold-rise postvaccination relative to D01 at D15 profile to the B.1.351 variant in each Intervention Group ≥ 2-fold-rise and ≥ 4-fold-rise in serum neutralization titer [post/pre] (fold-rise ≥ 2 and ≥ 4) at D15 relative to D01 profile to the B.1.351 variant in each study Intervention Group Seroresponse rate, defined as a 4-fold-or greater rise in serum neutralization titer [pre/post] at D15 relative to D01, profile to the B.1.351 variant in each study Intervention Group 
Endpoints for secondary objectives #15 and #16: neutralizing responses to be evaluated against the D614G strain and to the B.1.351 variant
 
 Individual serum neutralizing titers in each Intervention Group at each pre-defined timepoint Individual serum neutralization titer fold-rise postvaccination at each pre-defined timepoint relative to D01 in each Intervention Group ≥ 2-fold-rise and ≥ 4-fold-rise in serum neutralization titer [post/pre] (fold-rise ≥ 2 and ≥ 4) at each predefined timepoint relative to D01 in each study Intervention Group 
Endpoints for secondary objective #17:
 
 Individual serum neutralizing titer at D01 and D15 against the D614G strain in each Intervention Group Individual serum neutralization titer fold-rise postvaccination relative to D01 at D15 against the D614G strain in each Intervention Group ≥ 2-fold-rise and ≥ 4-fold-rise in serum neutralization titer [post/pre] (fold-rise ≥ 2 and ≥ 4) at D15 relative to D01 against the D614G strain in each study Intervention Group Seroresponse rate, defined as a 4-fold-or greater rise in serum neutralization titer [pre/post] at D15 relative to D01, against the D614G strain in each study Intervention Group Individual serum neutralizing titer at D01 and D15 profile to the B.1.351 variant in each Intervention Group Individual serum neutralization titer fold-rise postvaccination relative to D01 at D15 profile to the B.1.351 variant in each Intervention Group ≥ 2-fold-rise and ≥ 4-fold-rise in serum neutralization titer [post/pre] (fold-rise ≥ 2 and ≥ 4) at D15 relative to D01 profile to the B.1.351 variant in each study Intervention Group Seroresponse rate, defined as a 4-fold-or greater rise in serum neutralization titer [pre/post] at D15

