Safety Analysis Set (SafAS)	Participants randomized and who have received at least one dose of the study vaccines. All participants will have their safety data analyzed after each dose according to the vaccine they truly received, and after any dose according to the vaccine received at the first dose. Safety data recorded for participants not administered a study intervention will be excluded from the analysis (and listed separately).
Full analysis set (FAS)	All randomized participants who receive at least one study injection. Participants will be analyzed according to the intervention to which they were randomized.
Per-protocol analysis set (PPAS)	Subset of the FAS. Participants presenting with at least one of the following criteria will be excluded from the PPAS: 
 • Participant did not meet all protocol-specified inclusion criteria or met at least one of the protocol-specified exclusion criteria • Participants did not receive both injections for 2 doses primary vaccination groups or 1 dose booster injection for booster vaccination groups • Participant received a vaccine other than the one that he / she was randomized to receive • Preparation and / or administration of vaccine was not done as per-protocol • Participant did not receive protocol defined vaccine in the proper time window • Participants who did not provide all post-dose blood sample within the proper time window or no post-dose blood sample was drawn • Participant received the second injection (in the primary vaccination groups) despite meeting any of the definitive contraindication criteria • Participant receives an authorized/approved COVID-19 vaccine prior to D36 for primary vaccination groups or D15 for booster vaccination groups The definition may be complemented with additional criteria for exclusion after the review of protocol deviations reported on site.

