3.3.1 Analysis sets Used in Analyses

The analysis set used in analyses is listed in [Table 3.2](#).

Table 3.2: Analysis set used in analyses

Cohort	Type of Analyses		Intervention group(s)	Comparator group
Supplemental Cohort 1, Supplemental Cohort 2	Primary immunogenicity	Main	PPAS	PPAS Naïve at D01+D22
		Sensitivity	FAS	FAS Naïve at D01 FAS Naïve at D01+D22
	Secondary immunogenicity	Main	PPAS	PPAS Naïve at D01+D22
		Sensitivity	FAS	FAS Naïve at D01 FAS Naïve at D01+D22
	Exploratory immunogenicity regarding objective #11		PPAS	PPAS Naïve at D01+D22
	Exploratory immunogenicity in CMI subset for Cohort 2		CMIAS	CMIAS
	Exploratory immunogenicity in Variant Testing subset		VTAS Variant Testing Subset	VTAS Naïve at D01+D22 Variant Testing Subset Naïve at D01+D22
Supplemental Cohorts	Primary, Secondary safety		SafAS	SafAS

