3.4.7.3 Immunogenicity

No imputation of missing values and no search for outlier will be performed. LLOQ and ULOQ management will be performed as described in [Section 4.2.3.1](#).

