4.2 Complementary Information on Derived Endpoints: Calculation Methods

4.2.1 Safety

Main analysis, sensitivity analysis and complementary analysis will be undertaken based on safety analysis set. Main safety analysis will be performed as the key safety results, sensitivity and complementary analysis will be performed as supportive results. The rationale for conducting the sensitivity and complementary analysis is because of the high likelihood for participants in the study to receive a non-study authorized/approved COVID-19 vaccine for Supplemental Cohorts Comparator group, and for Supplemental Cohort 1 and Cohort 2 booster arms, in case the participants receive a non-study authorized/approval COVID-19 vaccine after booster dose. These study participants will be allowed to continue study participation if they choose to do so; while continuation in the study will include all study procedures including safety follow-up and therefore safety data will be collected after receipt of a non-study authorized/approved COVID-19 vaccine which will interfere with interpretation of the safety data following study vaccination.

Main analysis will be applied for all safety endpoints. It includes all adverse events or reactions with time of onset before the date of receiving a non-study authorized/approved COVID-19 vaccine (if applicable) during study period. For some selected endpoints, main analysis will only include safety data collected before the date of receiving a non-study authorized/approved COVID-19 vaccine (censored by the date) corresponding to those adverse events or reactions included. For the other endpoints, safety analysis will include all data collected in the entire collection period corresponding to those adverse events or reactions. Details of conducting main analysis for those endpoints including censored data are further clarified in the following subsections.

Sensitivity analysis will be conducted for some selected endpoints. It includes all adverse events or reactions with time of onset before receiving a non-study authorized/approved COVID-19 vaccine during the study period and includes safety data collected over the entire collection period corresponding to those adverse events or reactions. Details of conducting sensitivity analysis for those specific endpoints are further clarified in the following subsections.

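### No rule removes antibody samples drawn after a non-study COVID-19 vaccine received after D15/D36, so the late descriptive immunogenicity summaries can mix in another vaccine's effect

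*SAP*

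**What the plan says.** **Analysis sets (Section 3.3).** The per-protocol set (PPAS) lists one criterion on outside vaccination: "Participant receives an authorized/approved COVID-19 vaccine prior to D36 for primary vaccination groups or D15 for booster vaccination groups". The CMIAS and VTAS carry the same criterion. The full analysis set (FAS) is "All randomized participants who receive at least one study injection", with no condition on a non-study vaccine. The PPAS text also allows later additions: "The definition may be complemented with additional criteria for exclusion after the review of protocol deviations reported on site".

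**Which set is used (Table 3.2).** Secondary immunogenicity is analysed mainly on the PPAS (Comparator: "PPAS Naïve at D01+D22"), with the FAS as sensitivity.

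**Late objectives (Table 2.1).** Cohort 1 objective 17 is "To assess the neutralizing antibody profile to the D614G strain and to the B.1.351 variant at D29, D91, D181, and D366 overall" and by subgroup. Cohort 2 objective 15 is "To assess the neutralizing antibody profile to the D614G strain at D29, D91, D181, and D366 in each study Intervention Group", and objective 16 does the same for B.1.351. Objective 19 in each cohort covers binding antibody to D366, including responders.

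**Data handling.** Section 3.4.7.3 says "No imputation of missing values and no search for outlier will be performed" and points to the quantification-limit rules. Sections 4.2.3.1 to 4.2.3.3 (computed values, fold-rise, responders) place no condition on an intervening vaccine.

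**Safety and infection.** Section 4.2.1 justifies its extra analyses by "the high likelihood for participants in the study to receive a non-study authorized/approved COVID-19 vaccine for Supplemental Cohorts Comparator group", and for the booster arms by the possibility that it happens. Recipients may stay in the study with all procedures. The main safety analysis takes events with onset before the non-study vaccine. Section 4.2.2 applies the same start-date rule to the infection endpoints.

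**The concern.** The plan recognises non-study vaccination as something that disturbs interpretation and sets a date rule for safety and infection. A further COVID-19 vaccine acts directly on antibody titer, yet immunogenicity has no matching rule after D15 or D36.

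Take a booster participant vaccinated elsewhere on D60. The participant stays in the PPAS, and the D91, D181 and D366 titers enter the GMTs, fold-rises and binding responder rates as response to the study booster. The FAS treats those samples in the same way, so neither set isolates the persistence of the study vaccine, and comparing the two cannot reveal the problem. At stake are the descriptive durability results and, if uptake differs between groups, any late between-group GMT ratio produced under Section 3.4.4.

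**Working it through.** The plan states no figure on this point, so there is none to reproduce. The check has two parts.

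**1. Following one sample through the text.** Suppose a booster participant receives a non-study vaccine after D15 and gives blood at D91.
- PPAS, CMIAS and VTAS (Section 3.3): the dated criterion is not met, so the participant stays in.
- The separate criterion on receiving a vaccine other than the randomized one reads as an allocation error. If it also covered non-study vaccines, the dated criterion would be redundant.
- FAS: included.
- Missing data (3.4.7.3) and computed values (4.2.3.1): the titer is used as reported, subject only to LLOQ and ULOQ.
- Fold-rise (4.2.3.2): D91 value over D01 value, with no condition.
- Responders (4.2.3.3): also no condition.

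The sample therefore counts in both the main and the sensitivity analysis. The same holds at D29 for a vaccine received between D15 and D29. It also holds for Comparator blood drawn 4 to 12 months after the last injection (Section 1), if those visits are summarised.

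**2. Possible size.** Both inputs are assumptions, because the SAP gives neither:
- f = share of samples at a visit taken after a non-study vaccine;
- k = fold increase in titer caused by that vaccine.

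With μ the mean log10 titer without contamination:

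mean log10 titer = (1 − f)·μ + f·(μ + log10 k) = μ + f·log10 k

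The GMT is therefore multiplied by k^f. The D01 baseline comes first, so the geometric mean fold-rise has the same multiplier.

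| f | k=2 | k=5 | k=10 |
|---|---|---|---|
| 5% | 1.04 | 1.08 | 1.12 |
| 10% | 1.07 | 1.17 | 1.26 |
| 20% | 1.15 | 1.38 | 1.58 |
| 30% | 1.23 | 1.62 | 2.00 |
| 50% | 1.41 | 2.24 | 3.16 |

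*Share with a ≥4-fold rise.* Assume a true late geometric mean ratio of 2 and borrow the SD of 1.0 (log10) that Section 3.2.1 assumes for the post/pre ratio.
- Uncontaminated: 1 − Φ(log10 4 − log10 2) = 1 − Φ(0.301) = 38.2%.
- Among contaminated samples with k=10: 1 − Φ(log10 4 − log10 20) = 1 − Φ(−0.699) = 75.8%.
- Mixture at f=10%: 0.9 × 38.2% + 0.1 × 75.8% = 41.9%.
- Mixture at f=30%: 0.7 × 38.2% + 0.3 × 75.8% = 49.5%.

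*Two groups with shares f1 and f2 and the same k.* The GMT ratio is multiplied by k^(f1 − f2), which is 1 when uptake is equal.

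With samples on or after the non-study vaccination date removed, the multiplier from this source is 1.00 by construction.

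**The case against.** Several points on the other side stand.

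- **Hypothesis tests.** Every confirmatory comparison uses D15 and D36 titers, for which the cut-off is suitable. The late endpoints are descriptive.
- **Expected uptake.** The strong statement about uptake is made for the Comparator, whereas the late objectives in Table 2.1 concern the booster arms. There the SAP treats a non-study vaccine only as a contingency. Table 2.1 lists no secondary objective for late Comparator titers.
- **Low uptake.** At f of 5% to 10%, no multiplier in the table exceeds 1.26.
- **Between-arm bias.** The Cohort 2 main arms are randomized and observer-blinded, and nothing in the SAP suggests unequal uptake between them.
- **Safety handling.** Not every safety endpoint is fully censored. Events are selected by onset date, but data within a retained event are cut at the vaccine date only for selected endpoints.
- **Room to repair.** PPAS criteria may be added after deviation review, and Section 3.4 allows SAP amendments between the interim and final analyses.

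The last point does not close the gap. A criterion added after deviation review is not prespecified, and it would remove whole participants, including their valid D15 or D36 data. A deliberate choice to keep samples regardless of later vaccination could be defended, but the SAP does not state one, and it would fit the FAS rather than both sets.

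A reader might infer that the D91 to D366 results simply measure another vaccine or cannot be interpreted. The documents do not support that: only samples after such a vaccine are affected, so the summaries are a mixture of unknown proportion. A reader might also set the multipliers against 1.5. That figure is the margin for the D15-versus-D36 tests, and the SAP sets no threshold for persistence.

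**Conclusion.** The gap is real and worth closing, but limited in scope. As written, the descriptive immunogenicity summaries after D15/D36 count samples taken after another COVID-19 vaccine as study-vaccine persistence, in the PPAS and the FAS alike. The primary and alpha-controlled results are untouched.

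The size cannot be fixed from the SAP. Over assumed shares of 5% to 50% and assumed titer increases of 2- to 10-fold, a late GMT or geometric mean fold-rise is multiplied by 1.04 to 3.16. It is negligible at low uptake and large at high uptake. The upward direction rests on the assumption that another vaccine raises titers. Bias in between-group ratios further requires unequal uptake, which the documents do not show.

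It would be tempting to extend the point to samples after intercurrent infection, for which there is also no sample-level rule. Whether to drop those is a choice of estimand, so their retention is not treated here as an error.

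**What to change.** - Keep the PPAS as defined for D15 (booster) and D36 (Comparator).
- For every later visit, exclude from the PPAS, CMIAS and VTAS summaries any sample collected on or after the participant's first non-study COVID-19 vaccination. Keep the participant's earlier samples.
- Keep all samples in the FAS and name it as the sensitivity analysis for this question. Table 3.2 gives the CMIAS no companion set, so show the cellular and mucosal results with all samples as well.
- Report, by group and visit, how many samples the rule removes.
- Optionally, show late results with and without samples taken after a confirmed infection, as a sensitivity analysis only.

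The cost is SAP wording and a date-based flag on each sample. The first date of other COVID-19 vaccination is already used in Section 4.2.4.6. The downside is fewer late samples and possible informative censoring, since people who seek another vaccine may differ from those who do not. The comparison with the FAS helps to show this, although the two sets differ for other reasons too. The rule should be fixed by amendment before the database lock for the late visits.

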3.3.1 Analysis sets Used in Analyses

The analysis set used in analyses is listed in [Table 3.2](#).

Table 3.2: Analysis set used in analyses

Cohort	Type of Analyses		Intervention group(s)	Comparator group
Supplemental Cohort 1, Supplemental Cohort 2	Primary immunogenicity	Main	PPAS	PPAS Naïve at D01+D22
		Sensitivity	FAS	FAS Naïve at D01 FAS Naïve at D01+D22
	Secondary immunogenicity	Main	PPAS	PPAS Naïve at D01+D22
		Sensitivity	FAS	FAS Naïve at D01 FAS Naïve at D01+D22
	Exploratory immunogenicity regarding objective #11		PPAS	PPAS Naïve at D01+D22
	Exploratory immunogenicity in CMI subset for Cohort 2		CMIAS	CMIAS
	Exploratory immunogenicity in Variant Testing subset		VTAS Variant Testing Subset	VTAS Naïve at D01+D22 Variant Testing Subset Naïve at D01+D22
Supplemental Cohorts	Primary, Secondary safety		SafAS	SafAS

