3.3 Populations for Analyses

The following subgroup definitions of SARS-CoV-2 Naïve and Non-Naïve at D01 timepoint are applied for all randomized participants in all Supplemental Cohorts:

Prior SARS-CoV-2 infection status	Description
SARS-CoV-2 Naïve at baseline (Naïve-D01)	
• Negative by the anti-S immunoassay (Roche Elecsys) on D01 serum sample 
AND
 
• Negative NAAT for SARS-CoV-2 on respiratory sample collected on D01
SARS-CoV-2 Non-Naïve at baseline (Non-Naïve-D01)	
• Positive by the anti-S immunoassay (Roche Elecsys) on D01 serum sample 
OR
 
• Positive NAAT for SARS-CoV-2 on respiratory sample collected on D01

The following subgroup definitions of SARS-CoV-2 Naïve and Non-Naïve at both D01 and D22 timepoints are applied for all randomized participants in Supplemental Cohorts comparator groups:

Prior SARS-CoV-2 infection status	Description
SARS-CoV-2 Naïve at second injection (Naïve-D01+D22)	
• Negative by the anti-S immunoassay (Roche Elecsys) on D01 serum sample 
AND
 
• Negative NAAT for SARS-CoV-2 on respiratory sample collected on D01 and D22
SARS-CoV-2 Non-Naïve at second injection (Non-Naïve-D01/D22)	
• Positive by the anti-S immunoassay (Roche Elecsys) on D01 serum sample 
OR
 
• Positive NAAT for SARS-CoV-2 on respiratory sample collected on D01 or D22

The following populations are defined for analysis:

Population	Description
Screened	All participants screened for potential study enrollment will be included regardless of being enrolled or not being enrolled. The screening includes the SARS-CoV-2 rapid serodiagnosis test results, demographic information (age, ethnic/racial population, high-risk medical conditions), inclusion/exclusion criteria and prior vaccination platform for booster vaccination groups. The participants reaching the enrollment cap identified in IRT will be excluded from the study enrollment and will have no participant ID assigned.
Randomized	All participants with a randomized group that have been allocated by IRT.

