3.4.5 Secondary Endpoints - Safety

The occurrences of laboratory-confirmed symptomatic COVID-19 and serologically-confirmed SARS-CoV-2 infection will be described by percentages of participants with infection during the analysis period with 95% CI by Clopper-Pearson methods.

Participants with active SARS-CoV-2 infection at baseline (as determined by positive NAAT at D01) will be listed separately, if applicable.

If the total number of observed COVID-19 clinical illness cases collected during the analysis period is less than 5 in all groups, no summary analysis will be performed, and a listing of observed cases will be provided.

For Supplemental Cohorts Comparator group, laboratory-confirmed symptomatic COVID-19 and serologically-confirmed SARS-CoV-2 infection that occurred after authorized/approved COVID-19 vaccine injection will be listed separately.

For Supplemental Cohort 1 and Cohort 2 booster arms, laboratory-confirmed symptomatic COVID-19 and serologically-confirmed SARS-CoV-2 infection that occurred after authorized/approved COVID-19 vaccine injection during the study period will be listed separately.

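### The SAP has no rule removing D01 NAAT-positive participants from the booster sets, and none in either group for titers measured after an on-study infection

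*SAP*

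**What the plan says.** Table 3.2 (SAP 3.3.1) sets the main primary and secondary immunogenicity analyses as PPAS for the intervention groups and "PPAS Naïve at D01+D22" for the Comparator. The sensitivity rows have the same shape: plain FAS for the boosters, and FAS naïve at D01 or at D01+D22 for the Comparator.

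Under SAP 3.3, the Comparator restriction needs a negative anti-S result at D01 and "Negative NAAT for SARS-CoV-2 on respiratory sample collected on D01 and D22". That two-timepoint definition is "applied for all randomized participants in Supplemental Cohorts comparator groups". The D01 status has wider scope: the "subgroup definitions of SARS-CoV-2 Naïve and Non-Naïve at D01 timepoint are applied for all randomized participants in all Supplemental Cohorts". Table 3.2 does not use it for the booster arms.

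The only competing immune exposure among the PPAS exclusions is non-study vaccination: "Participant receives an authorized/approved COVID-19 vaccine prior to D36 for primary vaccination groups or D15 for booster vaccination groups". Infection is not named. The list is left open: "The definition may be complemented with additional criteria for exclusion after the review of protocol deviations reported on site".

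A positive swab on D01 is foreseen, but only under secondary safety (3.4.5): "Participants with active SARS-CoV-2 infection at baseline (as determined by positive NAAT at D01) will be listed separately, if applicable". Sections 4.2.2.1 to 4.2.2.4 define NAAT-confirmed, anti-N-confirmed and symptomatic infection as safety endpoints. The immunogenicity derivations (4.2.3) and the missing-data rule (3.4.7.3) do not refer to them.

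The persistence objectives run through twelve months. Cohort 1 secondary objective 17 (Table 2.1) reads: "To assess the neutralizing antibody profile to the D614G strain and to the B.1.351 variant at D29, D91, D181, and D366". Cohort 2 objectives 15 and 16 are similar.

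**The concern.** Two separate gaps follow.

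The first is between groups. A Comparator participant who is NAAT-positive at the second injection leaves the main analysis. A booster participant who is NAAT-positive at the booster injection is not removed by any rule in the SAP. If that infection adds to the D15 titer, it favours the booster in the non-inferiority test.

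The second is within each group. Infection acquired after injection can raise a later titer whatever the vaccine did, and the plan has no rule or sensitivity analysis for it. This affects the D15 post/pre ratio, and affects the D29 to D366 GMTs and fold-rises more, because infections accumulate. A twelve-month titer would then combine waning with infection, and no planned analysis separates them.

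The SAP itself treats infection history as relevant to titers. Section 5 restricts the Comparator for variant testing because serostatus may affect the response. Section 3.2.1 reports generally higher titers in non-naïve people after one dose than in naïve people after two.

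**Working it through.** **Which windows are screened, as written**

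| Window | Booster | Comparator (main set) |
|---|---|---|
| Day of last injection | D01 NAAT status defined, not used in Table 3.2 | D22 NAAT must be negative |
| 14 days before readout | D01–D15: no rule | D22–D36: no rule |
| After readout | no rule | no rule |

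The groups therefore differ mainly in the first row. If both have the same infected fraction f and the same extra log10 titer d in the 14-day window, the net shift in the between-group difference is f·d − f·d = 0. The shift in the booster's own post/pre ratio remains.

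**Check of the model against the plan's power**

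Inputs from SAP 3.2.1: log10 SD 1.0 (booster) and 0.65 (Comparator), margin 1/1.5, one-sided alpha 0.025/3 = 0.00833, attrition 3% and 10%.

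- Evaluable n: 0.97 × 515 → 499 (Cohort 2 Pfizer-primed), 0.97 × 215 → 208 (Cohort 1 Pfizer-primed), 0.90 × 515 → 463 (Comparator).
- Cohort 2: SE = √(1.0²/499 + 0.65²/463) = 0.0540. With a true ratio of 1, the distance to the margin is log10(1.5) = 0.176. Welch t power is 80.5% (Table 3.1: 80.5%).
- Cohort 1, true ratio 1.5: 98.7% (Table 3.1: 98.7%).

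**Shift at D15**

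If a fraction f of the booster arm carries an extra d log10, the mean log10 titer rises by f·d and the GMT is multiplied by 10^(f·d). Both f and d are assumptions. The columns give the one-sided false-positive rate when the truth lies exactly on the margin (nominal 0.0083), with SDs held fixed. Non-inferiority (NI) is at 1/1.5 and post/pre at 2.

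| f | d | GMT factor | NI, Cohort 2 | NI, Cohort 1 | Post/pre, Cohort 2 | Post/pre, Cohort 1 |
|---|---|---|---|---|---|---|
| 0.5% | 0.5 | 1.006 | 0.0094 | 0.0091 | 0.0097 | 0.0092 |
| 2% | 1.0 | 1.047 | 0.0215 | 0.0166 | 0.0257 | 0.0175 |
| 5% | 1.0 | 1.122 | 0.0708 | 0.0413 | 0.1002 | 0.0467 |

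For the NI columns, f is the excess in the booster arm, that is, infection at D01 with no counterpart in the Comparator. For the post/pre columns, f is infection that raises D15 but not D01.

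**Shift at late visits**

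The formula is the same, with f as assumed cumulative infection:

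- f = 5%, d = 0.5: 10^0.025 = 1.06
- f = 20%, d = 1.0: 10^0.20 = 1.58
- f = 30%, d = 1.0: 10^0.30 = 2.0

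**The case against.** **The Comparator restriction defines a population.** The objectives name naïve, unvaccinated people, and boosted participants are vaccinated by design. This stands for the anti-S part of the definition, and is why the naïve flag cannot be carried over to the booster arms. It does not explain why a positive D01 NAAT counts on one side only.

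**Eligibility may already remove these people.** The PPAS excludes anyone who breached the protocol's criteria, and the protocol is not at hand. A reader might infer that D01-positive booster participants certainly stay in the PPAS; the SAP cannot show that. It shows only that no rule of its own removes them and that it expects some to exist. Ineligibility does not remove anyone from the FAS, so the FAS rows would not expose the problem. The open clause on further exclusions depends on protocol deviations, and infection after injection is not in itself a deviation.

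**Infection after injection is treated alike.** A reader might infer that it is screened out of the Comparator and kept in the booster arms. The text does not support this for the period before readout or later, because Comparator screening ends at D22.

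**Direction.** Infection already active at D01 may have raised the D01 titer, in which case the post/pre ratio could fall. An upward bias in that ratio is plausible only for infection that raises titers after D01.

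**Size.** Every f and d is assumed. The post/pre test also has wide slack: the design ratio is 5 against a margin of 2, with stated power above 99.9% in the Pfizer-primed primary groups.

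**Estimand.** The persistence objectives are descriptive, and reporting all observed titers is a legitimate choice. This stands, so dropping titers after infection belongs beside the main analysis and need not replace it.

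**Conclusion.** The point holds in two parts. First, the SAP applies a NAAT rule at the last injection to the Comparator and none to the booster arms, so the non-inferiority comparison is unequal mainly for infection present on that day. Second, neither group has a rule or sensitivity analysis for titers after confirmed infection, so the D15 post/pre ratio and the D29 to D366 summaries mix infection with vaccine response.

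Under the assumed ranges the D15 effect is small to moderate, about 1.01- to 1.12-fold. The confirmatory test most exposed is Cohort 2 non-inferiority on B.1.351, where the assumed true ratio is 1 and power is 80.5%. At the margin its false-positive rate would be 0.0094 to 0.071 instead of 0.0083. Late GMTs could move about 1.06- to 2.0-fold, and persistence is the stronger practical reason to act. The documents do not show that any of these values will occur, and they do not show that a primary conclusion would change.

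**What to change.** 1. In Table 3.2, define the booster set for the confirmatory immunogenicity tests as the PPAS without participants NAAT-positive on D01. Use NAAT alone, not the anti-S-based naïve flag. This matches the rule at the Comparator's last injection.
2. Prespecify in both groups a sensitivity analysis of D15/D36 and all later timepoints. It drops titers from the first positive NAAT specimen or the onset of symptomatic COVID-19, or from the first anti-N-positive sample after an anti-N-negative one. Show it beside the all-titers analysis, with the number of samples removed per visit.

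The cost is SAP wording, slightly fewer evaluable samples (more at D366) and a small added derivation. Section 4.2.2.3 derives dates for symptomatic COVID-19 only. Asymptomatic NAAT-positive and serological cases need a date rule, and 4.2.2.2 counts any anti-N positive without requiring a change from negative. Table 8.1 lists no anti-N timepoints, so the available samples must be confirmed. Dropping titers after infection leaves a selected uninfected group at late visits, which is why both versions should be shown. Section 3.4 allows SAP amendments before later database locks.
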